Objectives	
 
To evaluate the safety and tolerability of APR-246 in combination with pembrolizumab in subjects with solid tumors.
 
To determine and confirm the maximum tolerated dose (MTD) for APR-246 in combination with 200 mg IV, every 3 weeks (Q3W) pembrolizumab in subjects with solid tumor malignancies.
 

	
 
Secondary objectives:         
 
Overall response rate (ORR) (Complete Response [CR] + Partial Response [PR]) of APR-246 in combination with pembrolizumab in subjects with solid tumor malignancies by Response Evaluation Criteria in Solid Tumors (RECIST) 1.1.
 
Progression-free survival (PFS) by RECIST 1.1.
 
Overall survival (OS).
 
Duration of response (DOR) by RECIST 1.1.
 
Disease control rate (DCR: CR + PR + stable disease [SD]) by RECIST 1.1
 
Durable SD rate (durable SD [SD ≥23 weeks]) by RECIST 1.1.
 
Clinical benefit rate (CBR: CR, PR + durable SD) by RECIST 1.1.
 
 
 
The pharmacokinetic (PK) profile of APR-246 during combination treatment with pembrolizumab.
 

	Exploratory objectives:
	1. To investigate the relationship between candidate efficacy biomarkers and anti- tumor activity of APR-246 in combination with pembrolizumab based on analyses of blood, serum, and/or tumor tissue.
Study	Primary endpoints:
Endpoints	
 
Occurrence of DLTs, classified and graded according to the National Cancer Institute's Common Terminology Criteria for Adverse Events (NCI-CTCAE, version 5.0).
 

 
Frequency of treatment-emergent adverse events (TEAEs), and serious adverse events (SAEs) related to APR-246 in combination with pembrolizumab.
 
RP2D of APR-246, defined as the dose of APR-246 at which < 2 out of 6 subjects experience DLT during the 3-week safety assessment period after the start of APR-246 administration in combination with pembrolizumab using dose de-escalation of APR-246.
 

Secondary endpoints:

 
ORR, defined as the proportion of subjects who have BOR of CR or PR measured by RECIST 1.1 (see APPENDIX V). ORR is measured from the start date of the treatment period until date of death from any cause. Subjects who are lost to follow-up and the subjects who are alive at the date of data cutoff will be censored at the date the subject was last known alive.
 
PFS, defined as the time from the first study dose date to the date of first
 

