Pembrolizumab is approved by the Food and Drug Administration (FDA) for melanoma, non-small cell lung cancer (NSCLC), bladder cancer, renal cancer, gastric/gastroesophageal junction (GEJ) adenocarcinoma, and other malignancies. Across indications, the approved dose and schedule of pembrolizumab is 200 mg IV over 30-minute infusion every 3 weeks. Warnings and precautions include immune-mediate pneumonitis, colitis, hepatitis, endocrinopathies, skin reactions, and infusion-related reactions. The most common adverse reactions (reported in  $\geq$  20% of patients) were: fatigue, musculoskeletal pain, decreased appetite, pruritus, diarrhea, nausea, rash, pyrexia, cough, dyspnea, constipation, pain, and abdominal pain. In combination with chemotherapy, adverse drug reactions (ADRs) included fatigue/asthenia, nausea, constipation, diarrhea, decreased appetite, rash, vomiting, cough, dyspnea, pyrexia, alopecia, and peripheral neuropathy. In combination

[figure not shown]
Aprea Therapeutics, Inc. Protocol Number A20-11195

with axitinib, ADRs included diarrhea, fatigue/asthenia, hypertension, hepatotoxicity, hypothyroidism, decreased appetite, palmar-plantar erythrodysesthesia, nausea, stomatitis/mucosal inflammation, dysphonia, rash, cough, and constipation. Table 1 in the United States Prescribing Information (USPI) provides recommended dose reductions of pembrolizumab in the setting of ADRs.

The PK of pembrolizumab was characterized using a population PK (popPK) analysis with concentration data collected from 2,993 patients with various cancers who received pembrolizumab doses of 1 to 10 mg/kg every 2 weeks, 2 to 10 mg/kg every 3 weeks, or 200 mg every 3 weeks. Steady-state concentrations of pembrolizumab were reached by 16 weeks of repeated dosing with an every 3-week (Q3W) regimen and the systemic accumulation was 2.1-fold. The Cmax, minimum concentration (Cmin), and AUC at steady state (AUCss) of pembrolizumab increased dose proportionally in the dose range of 2 to 10 mg/kg every 3 weeks.

Pembrolizumab CL% is approximately 23% lower [geometric mean, 195 mL/day (40%)] at steady state than that after the first dose [252 mL/day (37%)]; this decrease in CL with time is not considered clinically important. The terminal half-life ( $t_{1/2}$ ) is 22 days (32%).

[figure not shown]

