# 6.1.1 Dose-Limiting Toxicity

A DLT is defined as any of the following:

- Any of the hematological or nonhematological toxicities noted in the table below considered to be at least possibly related to APR-246 occurring during the 3-week safety assessment period after the start of APR 246 administration in combination with pembrolizumab (Cycle 1 Day 1).
- Failure to administer ≥75% of the planned dosage of APR-246 as a result of treatment-related toxicity during Cycle 1, unless reversible CNS-related effects previously described for APR-246.
- Subjects who discontinue treatment due to treatment-related toxicity.
- Greater than 4-week delay in starting Cycle 2 because of a treatment-related toxicity, even if the toxicity does not meet DLT criteria.

Dose-Limiting Toxicities	5 · · · · · · · · · · · · · · · · · · ·
Toxicity Category	Toxicity CTCAE Grade
Hematologic	Grade 4 neutropenia for ≥ 7 days
	Grade 3 or Grade 4 febrile neutropenia a
	Thrombocytopenia <25,000/mm  associated with bleeding and/or that
	requires platelet transfusion
Other nonhematologic	Any other Grade 4 or a Grade 5 toxicity
toxicity	Grade 3 toxicities lasting > 3 days excluding:
	Nausea, vomiting, fatigue and diarrhea controlled by medical
	intervention within 72 hours.
	Grade 3 rash in the absence of desquamation, no mucosal involvement,
	does not require steroids, and resolves to Grade 1 by the next
	scheduled dose of pembrolizumab.
	Grade 3 hypertension not able to be controlled by medication
	Grade 3 or above gastrointestinal perforation
	Grade 3 or above wound dehiscence requiring medical or surgical
	intervention
	Any grade thromboembolic event
	Any Grade 3 non-hematologic laboratory value if: Medical intervention is
	required to treat the subject, or the abnormality leads to hospitalization
ANC = absolute neutrophil cour	nt, CTCAE = Common Terminology Criteria for Adverse Events v5.0.
a Febrile neutropenia Grade 3 o	
	00/mm  with a single temperature of >38.3 °C (101 °F) or a sustained temperature of ≥ 38 °C
(100.4 °F) for more than one ho Grade 4 is defined as ANC < $100$	ur. )0/mm³ with a single temperature of >38.3 °C (101 °F) or a sustained temperature of ≥ 38 °C
	ur, with life-threatening consequences and urgent intervention indicated

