# 8.1.2 Reporting of Adverse Events

#### 8.1.2.1 Adverse Events

An AE is any untoward medical occurrence in a subject or clinical investigation subject administered a pharmaceutical product that does not necessarily have a causal relationship with the treatment. An AE can be any unfavorable and unintended sign (including a laboratory finding), symptom or disease temporally associated with the use of a medicinal (investigational) product, whether or not related to the medicinal (investigational) product.

The AE reporting period starts at study treatment initiation. At each evaluation, subjects should be interviewed in a non-directed manner to elicit potential adverse reactions from the subject. The occurrence of an AE will be based on changes in the subject's physical examination, laboratory results, and/or signs and symptoms.

All AEs (except Grade 1 and 2 laboratory abnormalities that do not require an intervention), regardless of causal relationship, are to be recorded in the eCRF and source documentation. The investigator must determine the intensity of any AEs according to the NCI-CTCAE version

5.0 and their causal relationship. Those AEs not covered by these criteria will be graded as follows:

- 1. Mild: Discomfort noticed, but no disruption of normal daily activity. Prescription drug not ordinarily needed for relief of symptom but may be given because of personality of subject.
- 2. Moderate: Discomfort sufficient to reduce or affect normal daily activity. Subject is able to continue in study; treatment for symptom may be needed.
- 3. Severe: Incapacitating, severe discomfort with inability to work or to perform normal daily activity. Severity may cause cessation of treatment with test drug; treatment for symptom may be given and/or subject hospitalized.
- 4. Life-Threatening: Symptom(s) place the subject at immediate risk of death from the reaction as it occurred; it does not include a reaction that, had it occurred in a more serious from, might have caused death.
- 5. Fatal: Event caused the death of the subject.

AEs will be followed until resolution or stabilization while the subject remains on-study. Once the subject is removed from study, events thought to be related to the study medication will be followed until resolution or stabilization, unless, in the investigator's opinion the event is unlikely to resolve due to the subject's underlying disease, or until the subject starts a new treatment regimen or the subject is lost to follow-up.

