# 8.1.2.4 Serious Adverse Event (SAE)

An SAE is defined as any untoward medical occurrence that at any dose:

- 1. Results in death,
- 2. Is life-threatening (i.e., the subject was at risk of death at the time of the event. It does not refer to an event which hypothetically might have caused death if it was more severe),
- 3. Requires inpatient hospitalization or prolongation of existing hospitalization excluding that for pain management, disease staging/re-staging procedures, or catheter placement unless associated with other serious events,
- 4. Results in persistent or significant disability/incapacity, or
- 5. Is a congenital anomaly/birth defect.

Important medical events that may not result in death, be life-threatening, or require hospitalization may be considered serious adverse drug events when, based on appropriate medical judgment, they may jeopardize the subject and may require medical or surgical intervention to prevent one of the outcomes listed above.

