# 8.1.2.6 Reporting of Serious Adverse Events

AEs classified as serious require expeditious handling and reporting to Sponsor's monitoring CRO to comply with regulatory requirements.

For any SAE that occurs while a subject is on-study; within 30 days of the last study treatment administration, regardless of any opinion as to the relationship of the SAE to the study treatment; or if any SAE that the investigator feels is related to the study treatment occurs later than 30 days after the last study treatment administration, the Sponsor's monitoring CRO must be notified immediately (within 24 hours of becoming aware of the event) by email, fax or telephone. Notification by email is preferred. The email address, fax and telephone numbers listed below may be used during both business and non-business hours. During non-business hours a recorded message will provide the telephone caller with the contact information for the on-call monitor.

All SAEs require that a Serious Adverse Event Report Form be completed and forwarded either via facsimile or as a PDF via email to Sponsor's monitoring CRO at the fax number or email listed below within 24 hours of becoming aware of the event.

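### The SAE definition exempts admissions for pain management without limiting this to planned admissions or pre-existing cancer pain, so an isolated admission for new or worsening pain can escape the related-SAE count and the 24-hour notice

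*Combined protocol and SAP*

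**What the plan says.** Section 8.1.2.4 lists five seriousness criteria. Item 3 is inpatient hospitalization or its prolongation, "excluding that for pain management, disease staging/re-staging procedures, or catheter placement unless associated with other serious events". No further condition is attached to the pain exemption. After the list, a general sentence covers important medical events that meet none of the five outcomes: they "may be considered serious adverse drug events when, based on appropriate medical judgment, they may jeopardize the subject".

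Three other parts of the plan bear on this:

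- **Endpoint.** The synopsis gives as a primary endpoint: "Frequency of treatment-emergent adverse events (TEAEs), and serious adverse events (SAEs) related to APR-246 in combination with pembrolizumab".
- **Reporting.** Section 8.1.2.6 requires SAEs on study or within 30 days of last treatment to be notified within 24 hours of awareness, whatever the view on cause. After 30 days, only SAEs that the investigator considers related must be notified.
- **Recording.** Section 8.1.2.1 says that AEs, apart from minor laboratory abnormalities, "regardless of causal relationship, are to be recorded in the eCRF and source documentation".

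Section 2.4 lists the reactions reported in at least 20% of pembrolizumab patients: "fatigue, musculoskeletal pain, decreased appetite, pruritus, diarrhea, nausea, rash, pyrexia, cough, dyspnea, constipation, pain, and abdominal pain". Three of these are forms of pain.

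**The concern.** The three exempted purposes are not alike. Staging and catheter placement are procedures that need not involve any untoward event. Pain management treats a symptom, and that symptom may be a new adverse reaction. The exemption turns on why the bed was used. It does not ask whether the pain was there before dosing, whether it got worse, or what caused it.

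Pain is a listed reaction of one of the two study drugs, so the case is foreseeable in this trial. Two things are at stake. The first is the related-SAE frequency, which would be biased downward for this type of event. The second is speed: SAE status triggers the 24-hour notice and the Medical Monitor's review of SAEs as they come in (8.1.2.7).

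**Working it through.** The plan states no figure on this point, so there is none to reproduce. The check is to follow one case through the rules.

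**Case.** A subject on study is admitted solely for control of new abdominal pain that the investigator judges possibly related to treatment. There is no other serious event.

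1. *Hospitalization criterion (8.1.2.4 item 3).* The admission is for pain management, so it is exempt. The closing exception needs another serious event, and there is none. The sentence also leaves unclear whether that exception governs all three exclusions or only catheter placement.
2. *Other criteria (8.1.2.4 items 1, 2, 4 and 5).* Death, threat to life, lasting or significant disability, and birth defect do not apply.
3. *Important medical event (8.1.2.4, last paragraph).* This route is open but permissive. It asks whether intervention may be needed to prevent a listed outcome, and the listed hospitalization outcome already leaves out pain admissions. Two investigators could reasonably classify the same case differently.
4. *24-hour notice (8.1.2.6).* This applies to SAEs. If step 3 is not used, no notice is due.
5. *TEAE count (8.1.2.1).* The event is recorded, graded and assessed for causality, so it enters the TEAE part of the primary endpoint. Table 4 and Section 7.3 run toxicity assessment to 30 days after last dose. Section 6.3.4.2 says that immune-related events may appear several months after the last pembrolizumab dose. A late case of this kind could therefore miss both the TEAE record and the SAE notice.
6. *DLT count (6.1.1).* This applies only in the lead-in and Cycle 1. The table's main route for such an event is "Grade 3 toxicities lasting > 3 days excluding" certain listed toxicities. Pain is not among those exclusions, so Grade 3 pain lasting more than 3 days and at least possibly related to APR-246 would qualify. Shorter Grade 3 pain would not qualify by that route. It could still qualify through discontinuation for treatment-related toxicity, through less than 75% of planned APR-246 being given because of toxicity, or through a delay of more than 4 weeks to Cycle 2.

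The case can thus end as a TEAE without the serious flag and without expedited notice.

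**Size.** One event in a cohort of 20 is 1/20 = 5 percentage points of that cohort's SAE rate. The number of such events needs a rate r of isolated, treatment-related admissions for pain control alone, and the documents give none. The list in Section 2.4 has neither grades nor admissions. The sums below only show how far the answer depends on the assumption:

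- Maximum N = 18 + 100 = 118. With 20 per cohort and one lead-in level of 6, N = 3 × 20 + 6 = 66.
- Expected events = N × r. Chance of at least one = 1 − (1 − r)^N.
- Assumed r = 1%: 66 × 0.01 = 0.66 events and 48% at N = 66; 118 × 0.01 = 1.2 events and 69% at N = 118.
- Assumed r = 5%: 66 × 0.05 = 3.3 events and 97% at N = 66; 118 × 0.05 = 5.9 events and 99.8% at N = 118.

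Even at a given r these are upper figures, because some cases would be caught at steps 2 and 3. They are not estimates for this trial.

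**The case against.** A reader might infer that every hospitalization for treatment-related pain drops out of the primary endpoint and goes unreported. The documents do not support that, for four reasons:

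- The exemption has its own exception, the other four criteria remain in force, and the investigator may still class the event as serious.
- The exemption concerns admission for pain management. Section 6.3.4.2 calls for evaluation of suspected immune-related events to establish their cause, with endoscopy or biopsy where needed. An admission to investigate or treat the cause of abdominal pain is not plainly an admission for pain management.
- The same primary endpoint counts TEAEs, so during the AE reporting period only the serious flag is lost.
- Review does not depend on SAE status alone. Under Section 8.1.2.7 the Data Review Team looks at AEs and DLTs and discusses all accumulated safety data, and the Medical Monitor reviews safety data periodically.

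It is also fair to say that no decision rule uses the SAE count. Section 9.3 summarizes safety data without a formal test, and the RP2D rests on DLTs.

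All of this stands, and it narrows the point to isolated admissions for pain control. It does not remove the point. The important-medical-event sentence is optional, the TEAE record neither triggers the 24-hour notice nor enters the related-SAE count, and the Data Review Team meets at a frequency that depends on accrual.

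**Conclusion.** The point holds in a limited form. As written, item 3 lets an isolated admission for control of new or worsening pain, including treatment-related pain, fall outside the related-SAE frequency and the 24-hour notice, unless another criterion is met or the investigator chooses the discretionary route. Any bias in the related-SAE count is downward. Its size cannot be stated from the documents.

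The conclusion rests on reading the pain exemption as it stands, without a restriction that the text does not contain. It does not depend on any assumed admission rate. This is a defect in a safety-reporting definition that feeds a primary endpoint. It does not touch the dose-finding rule or the efficacy analysis.

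**What to change.** Amend Section 8.1.2.4 item 3 in three respects:

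1. Limit the pain exemption to admissions planned before first dose, or for pre-existing cancer pain that has not worsened since first dose.
2. State that an admission for new or worsening pain on study is an SAE whatever the causality opinion, with relatedness assessed separately under Section 8.1.2.2. Making seriousness depend on relatedness would sit badly with Section 8.1.2.6, which requires SAEs on study or within 30 days of last treatment to be reported whatever the view on cause.
3. State whether the exception for association with other serious events covers all three exclusions or only catheter placement.

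Leave the staging and catheter exclusions unchanged. Causality is already collected, so no new assessment is needed. The cost is a short protocol edit, a slightly higher SAE count and a few more expedited reports, some of them for disease-related pain.

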# 8.1.2.5 Pregnancy

Any pregnancy detected during the study, or that occurs within 30 days after stopping study medication, must be reported immediately to the investigator. Pregnancy, in and of itself, is not regarded as an AE, unless there is suspicion that study medication may have interfered with the effectiveness of a contraceptive medication. If the subject becomes pregnant while on-study, the study drug should be immediately discontinued. Pregnancy information about a female subject or a female partner of a male subject should be reported immediately from the time the investigator first becomes aware of a pregnancy or its outcome. This will be performed by the investigator per instructions from the Sponsor's monitoring CRO.

Any pregnancy complication, spontaneous abortion, elective termination of a pregnancy for medical reasons, outcome of stillbirth, congenital anomaly/birth defect, or SAE in the mother will be recorded as an SAE and will be reported as described in Section 8.1.2.6.

# 8.1.2.6 Reporting of Serious Adverse Events

AEs classified as serious require expeditious handling and reporting to Sponsor's monitoring CRO to comply with regulatory requirements.

For any SAE that occurs while a subject is on-study; within 30 days of the last study treatment administration, regardless of any opinion as to the relationship of the SAE to the study treatment; or if any SAE that the investigator feels is related to the study treatment occurs later than 30 days after the last study treatment administration, the Sponsor's monitoring CRO must be notified immediately (within 24 hours of becoming aware of the event) by email, fax or telephone. Notification by email is preferred. The email address, fax and telephone numbers listed below may be used during both business and non-business hours. During non-business hours a recorded message will provide the telephone caller with the contact information for the on-call monitor.

All SAEs require that a Serious Adverse Event Report Form be completed and forwarded either via facsimile or as a PDF via email to Sponsor's monitoring CRO at the fax number or email listed below within 24 hours of becoming aware of the event.

# 8.1.2.7 Safety Monitoring Plan

The Medical Monitor is responsible for ongoing safety monitoring for the study per the detailed safety plan. This monitoring will include a review of all SAEs as they are reported by the study site. The Medical Monitor will also be in contact with site monitors and will be available to discuss any issues concerning safety with site staff. Safety data will be reviewed periodically by the **Medical Monitor methods** and the Sponsor's Medical Officer.

DRT consisting of the Medical Monitor, Site Principal Investigators, and other clinical research personnel that the Sponsor may deem appropriate, will hold DRMs on an interim basis at a frequency dependent on study accrual. At these meetings, the DRT will review AEs and DLTs and make recommendations regarding the RP2D. In the expansion portion of the study, the DRT will evaluate safety and tolerability after 5 subjects have completed 1 cycle of treatment in each cohort. All accumulated safety data will be discussed during DRMs.

The DRT will produce summaries or minutes of these meetings. These summaries will be available for inspection when requested by any of the regulatory bodies charged with the safety of human subjects and the integrity of data.

